5.1.3. EXPOSURE TIME

Time at risk will start on index date and continue until first treatment discontinuation (see definition in Section 5.1.6). Continuous exposure will be defined as successive exposure periods for the study drugs separated by gaps of 30 days at most. Duration of exposure

Proprietary confidential information © 2024 Boehringer Ingelheim International GmbH or one or more of its affiliated companies

episodes for individual prescriptions of study drugs will be derived based on package size, unit strength and daily dose.

To account for an empirical induction/promotion period of cancer, a latency period of 6 months (180 days) after the index date is applied. Patients with less than 6 months (180 days) of follow-up time will be excluded. In addition, patients with any diagnosis of any cancer within the latency period will be excluded. In a sensitivity analysis, the latency period will be extended to 12 months (365 days).

* Other drugs: a prescription of another drug (empagliflozin, a DPP-4 inhibitor, or a SGLT-2 inhibitor) other than index drug

Figure 1 Definition of continuous exposure period of index drug

For the primary AT analyses, the time at risk will begin after the latency period and end at urinary tract (bladder, renal or other) cancer or at any of the censoring events (listed in Table 4), whichever occurs first. In addition, treatment discontinuation of the index drug (defined in Section 5.1.6) is an additional censoring variable.

For the sensitivity ITT analyses, the time at risk will begin after the latency period and end at urinary tract (bladder, renal or other) cancer or any of the censoring events excluding treatment discontinuation of the index drug.

Patients with censored time at risk will not be able to re-enter the study cohort at a later time point. The time at risk will not be censored if oral or injectable glucose-lowering drugs other than the index drugs and SGLT-2 inhibitors are prescribed in addition to empagliflozin or a DPP-4 inhibitor after the index date.

Proprietary confidential information © 2024 Boehringer Ingelheim International GmbH or one or more of its affiliated companies

Table 4 Censoring events.

Censoring event	Definition	Data source
All-cause mortality	Censoring of follow-up time occurs at the date of death regardless of the cause. Applied in all analyses.	UK: CPRD-GOLD and Aurum Sweden: Cause of death register Finland: Cause of death register

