Emigration from the study country	Censoring of follow-up time occurs at the date of emigration from the study country. Applied in all analyses.	UK: CPRD-GOLD and Aurum Sweden: Total population register ¹ Finland: Population register centre
Patient transfer	Censoring of follow-up time occurs at the date of patient transfer. Applied in all analyses.	UK: CPRD-GOLD and Aurum Sweden: NA Finland: NA
Incidence of any cancer during follow-up	A registered diagnosis of any cancer (excluding non-melanoma skin cancer) during follow-up. (ICD-10, ICD-7, ICD-O-3 and READ diagnosis codes in Annex I) Applied in all analyses.	UK: CPRD-GOLD and Aurum Sweden: Swedish cancer registry (SCR) Finland: FCR
Diabetes diagnosis other than type 2	A diagnosis of type 1 diabetes or other non-type 2 diabetes during follow-up identified using the same algorithm as used for the exclusion criteria (Section 4.2.4) Relevant ICD-10 codes and READ diagnosis codes are provided in Annex I. Applied in all analyses.	UK: CPRD and Aurum Sweden: NDR, NPR Finland: reimbursement registry
End of study period	Censoring of follow-up time occurs at end of study date i.e. 31 December 2020 (2021 for UK-CPRD). Applied in all analyses.	NA

Proprietary confidential information © 2024 Boehringer Ingelheim International GmbH or one or more of its affiliated companies

Treatment discontinuation (AT exposure- main analysis)	Censoring of follow-up time occurs 90 days after 
 - last day of medication (i.e. stop date) - new prescription of the other study drug or of a SGLT-2 inhibitor Applied only in analyses using the AT exposure definition.	UK: CPRD-GOLD and Aurum Sweden: SPDR Finland: FPR
Treatment discontinuation (AT exposure- sensitivity analysis)	Censoring of follow-up time occurs 180 days after 
 - last day of medication (i.e. stop date) - new prescription of the other study drug or of a SGLT-2 inhibitor Applied only in the sensitivity analysis using the AT exposure definition.	UK: CPRD-GOLD and Aurum Sweden: SPDR Finland: FPR

¹ The National patient register will be used if data on immigration/emigration are unavailable from the Total population register.

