5.1.7. Primary Exposure definition

The primary definition of exposure, i.e. as-treated exposure (AT), is defined as a continuous exposure to empagliflozin or to a DPP-4 inhibitor, starting from index date. Continuous exposure and treatment discontinuation are defined in Section 5.1.6.

In the Swedish dataset, drug exposure will be identified from SPDR. In Finland, the FPR will be used. In the UK datasets, drug exposure will be identified from CPRD data. The study drugs will be identified using ATC codes (med codes for CPRD) listed in Annex II.

Proprietary confidential information © 2024 Boehringer Ingelheim International GmbH or one or more of its affiliated companies

Table 5 As-treated exposure definition

Exposure	Definition	Details	Data source
Exposure to index drugs (as treated)	Exposure status for empagliflozin (alone or in combination with metformin) or DPP-4 inhibitor (including combinations) based on purchased amounts and daily defined dose. ATC codes for empagliflozin and DPP-4 inhibitors in Annex II.	Time-fixed Categorical: Empagliflozin DPP-4 inhibitor	UK: CPRD Sweden: SPDR Finland: FPR
Evaluated at index date			

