5.1.8. SECONDARY EXPOSURE DEFINITIONS

Exposure definitions based on dosage or duration

Table 6 Exposure definitions based on dosage or duration

Exposure	Definition	Details	Data source
Cumulative dose of empagliflozin use in grams	Time-updating cumulative sum of empagliflozin dose consumption based on the daily prescribed dose and purchased amounts since the start of follow-up. ATC codes for empagliflozin in Annex II.	Time-dependent Categorical ¹ : Never 0 - <cumulative dose Q1 ≥ Q1 to < Q2 ≥ Q2 to < Q3 ≥ Q3	UK: CPRD Sweden: SPDR Finland: FPR
Daily dose of empagliflozin	The dosage of empagliflozin prescribed per daily use (10mg vs. 25mg). ATC codes for empagliflozin in Annex II.	Time-dependent Categorical: Never 10 mg 25 mg	UK: CPRD Sweden: SPDR Finland: FPR
Updating from index date onwards.*			

Proprietary confidential information © 2024 Boehringer Ingelheim International GmbH or one or more of its affiliated companies

Cumulative exposure duration to empagliflozin in months	Time-updating cumulative sum of duration since the first use of empagliflozin (alone or in combination with metformin), in months. ATC codes for empagliflozin in Annex II.	Time-dependent Categorical ² : Never 0 - < cumulative duration Q1 Updating from index date onwards.* ≥ Q1 to < Q2 ≥ Q2 to < Q3 ≥ Q3	UK: CPRD Sweden: SPDR Finland: FPR
---	--	--	--

*The last observed value will be carried forward for 3 months (90 days) to account for the 90-day delay between end of treatment and treatment discontinuation as defined in Section 5.1.6.

¹ The categories are defined based on the quartiles of overall cumulative dose (grams) of the study population

² The categories are defined based on the quartiles of overall cumulative exposure duration (months) of the study population

Intention-to-treat exposure definition

The intention to treat exposure definition assumes that individuals do not discontinue the treatment of an index drug.

Table 7 Intention-to-treat exposure definition

Exposure	Definition	Details	Data source
Exposure to index drugs (Intention to treat)	Purchase of empagliflozin (alone or in combination with metformin) or any DPP-4 inhibitors (including combinations). ATC codes for empagliflozin and DPP-4 inhibitors in Annex II.	Time-fixed Categorical: Empagliflozin	UK: CPRD Sweden: SPDR Finland: FPR

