Hazard ratio estimates using adjusted model	
Using matched cohorts
 
Stratified by gender.
 
(18 tables, 3 outcomes x 2 strata by gender x 3 countries)
	As treated exposure definition	Main outcomes- Table 8	Table 25
Hazard ratio estimates using adjusted model	
Using matched cohorts
 
Stratified by insulin use at index.
 
(18 tables, 3 outcomes x 2 strata by insulin use at index x 3 countries)
	As treated exposure definition	Main outcomes- Table 8	Table 25
Meta-analyses for adjusted HR estimates	
Using adjusted HR estimates and 95% CIs from all study countries.
 
For each stratification variable listed above.
 
(54 figures, 3 outcomes x (3+4+7+2+2) strata)
	As treated exposure definition	Main outcomes- Table 8	Figure 8
Secondary objectives:				
Descriptive analysis				

Analysis	Details	Exposure definition	Outcomes	Template
Stratified incidence rates	Using matched cohorts Country specific analysis (9 tables, 3 outcomes x 3 countries)	Cumulative exposure dose of empaglifloz in	Main outcomes- Table 8	Table 30
Stratified incidence rates	Using empagliflozin users subgroup Country specific analysis (9 tables, 3 outcomes x 3 countries)	Empaglifloz in daily dose	Main outcomes- Table 8	Table 31
Stratified incidence rates	Using empagliflozin users subgroup Country specific analysis (9 tables, 3 outcomes x 3 countries)	Cumulative exposure duration to empaglifloz in	Main outcomes- Table 8	Table 32
Meta-analysis of incidence rates	Using pooled number of outcome events and person-time from all study countries (9 tables, 3 outcomes x 3 secondary exposure definitions)	The secondary exposure definitions listed above	Main outcomes- Table 8	Table 30- Table 32
Secondary objectives: Comparative analysis				
Hazard ratio estimates using adjusted model	Using matched cohorts Country specific analysis (9 tables, 3 outcomes x 3 countries)	Cumulative exposure dose of empaglifloz in	Main outcomes- Table 8	Table 26
Hazard ratio estimates using adjusted model	Using matched cohorts Country specific analysis (9 tables, 3 outcomes x 3 countries)	Empaglifloz in daily dose	Main outcomes- Table 8	Table 27

Analysis	Details	Exposure definition	Outcomes	Template
Hazard ratio estimates using adjusted model	Using matched cohorts Country specific analysis (9 tables, 3 outcomes x 3 countries)	Cumulative exposure duration to empagliflozin	Main outcomes- Table 8	Table 28

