Meta-analysis of adjusted HR estimates	Using adjusted HR estimates with 95% CIs from all study countries (9 figures, 3 outcomes x 3 secondary exposure)	3 secondary exposure definitions listed above	Main outcomes- Table 8	Figure 8

Sensitivity analysis: NCC study design

Balance assessment for baseline characteristics between matched cases and controls.	Country specific analysis (3 tables, one for each country)	N/A	N/A	Table 33
Odds ratio using conditional logistic regression	Nested case-control study design. (3 tables, 1 outcome (all cancer cases) x 3 countries)	As treated exposure definition	All cancer cases defined in Table 8	Table 34
Meta-analysis for odds ratio estimates	Using odds ratio estimates with 95% CIs from all study countries (1 figure, 1 outcome (all cancer cases))	As treated exposure definition	All cancer cases defined Table 8	Figure 8

Analysis	Details	Exposure definition	Outcomes	Template
Sensitivity analysis: Adjusting for time-dependent confounding				
Hazard ratio estimates using marginal structural model	Using matched cohorts MSM using IPTW. (3 tables, 1 outcome x 3 countries)	As treated exposure definition	Urinary tract cancer as defined in Table 8	Table 35
Meta-analysis of adjusted HR estimates using MSM	Using adjusted HR estimates with 95% CIs from all study countries (1 figure, 1 outcome)	As treated exposure definition	Urinary tract cancer as defined in Table 8	Figure 8
Sensitivity analysis: Exposures				
Hazard ratio estimates using adjusted model	Using matched cohorts (3 tables, 1 outcome x 3 countries)	Intention to treat exposure definition	Urinary tract cancer as defined in Table 8	Table 25
Meta-analysis of adjusted HR estimates	Using adjusted HR estimates with 95% CIs from all study countries (1 figure, 1 outcome)	Intention to treat exposure definition	Urinary tract cancer as defined in Table 8	Figure 8
Sensitivity analysis: Grace period				
Hazard ratio estimates using adjusted model	Using matched cohorts Allowed gaps between exposure episodes extended to 90 days (3 tables, 1 outcome x 3 countries)	Intention to treat exposure definition	Urinary tract cancer as defined in Table 8	Table 25
Meta-analysis of adjusted HR estimates	Using adjusted HR estimates with 95% CIs from all study countries (1 figure, 1 outcome)	Intention to treat exposure definition	Urinary tract cancer as defined in Table 8	Figure 8

Analysis	Details	Exposure definition	Outcomes	Template
Sensitivity analysis:				
Outcomes				

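### For the three secondary exposure analyses the SAP is inconsistent on censoring at stopping or switching, and on its natural reading DPP-4 initiators who start empagliflozin add unlagged exposed time

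*SAP*

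**What the plan says.** Four parts of the SAP bear on when follow-up ends in the dose and duration analyses.

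- **Table 4 (5.1.3).** Censoring 90 days after the stop date, or after a new prescription of the other study drug, is "Applied only in analyses using the AT exposure definition".
- **Section 5.1.7.** "The primary definition of exposure, i.e. as-treated exposure (AT), is defined as a continuous exposure to empagliflozin or to a DPP-4 inhibitor". Table 5 makes it time-fixed. The dose and duration variables are set out separately in 5.1.8 and Table 6 as secondary, time-dependent definitions.
- **Table 16 (6.10).** The secondary rows name cumulative dose, daily dose and cumulative duration as the exposure definition. The pooled row refers to the "3 secondary exposure definitions listed above". None is labelled as-treated.
- **Opening of 5.1.3 and the Table 6 footnote.** The first says "Time at risk will start on index date and continue until first treatment discontinuation", without limiting this to one analysis. The second says of the dose and duration variables: "The last observed value will be carried forward for 3 months (90 days) to account for the 90-day delay between end of treatment", and it refers to treatment discontinuation as defined in 5.1.6.

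On the lag, 5.1.3 says that "a latency period of 6 months (180 days) after the index date is applied". On duration, Table 6 gives "Time-updating cumulative sum of duration since the first use of empagliflozin (alone or in combination with metformin), in months". No visible text states a lag from first empagliflozin use for a patient whose index drug was a DPP-4 inhibitor. Protocol 8.3.4 states discontinuation censoring for the primary AT analysis and does not mention the dose and duration analyses.

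**The concern.** Two programmers could build different risk sets for the secondary objectives from the same SAP. One would censor at stop or switch plus 90 days. The other, following Table 4 word for word, would not.

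Without that censoring, a patient who stops empagliflozin stays at risk after the carry-forward ends, and daily dose (Never, 10 mg, 25 mg) then has no category for them. A DPP-4 initiator who starts empagliflozin adds exposed time with no limit other than the remaining censoring events.

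With that censoring, a smaller asymmetry remains. The variables are time-dependent and update on empagliflozin use, so a switcher's first days on empagliflozin count as exposed. For an empagliflozin initiator the first 180 days are removed. The low-exposure hazard ratio would then mix lagged and unlagged time, and days that the primary analysis assigns to DPP-4 would be assigned to empagliflozin.

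**Working it through.** The plan gives no figure on this point to reproduce. The check compares texts, does day arithmetic on the stated windows, and adds an illustrative size.

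**1. Which results are affected.** In Table 16 the secondary hazard ratio models use the matched cohorts, and Tables 26-28 take never-exposed patients as reference, so DPP-4 initiators are in these models. The cumulative-dose incidence rates also use the matched cohorts. The daily-dose and duration incidence rates are listed for the empagliflozin users subgroup, so the switcher question does not arise there.

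**2. Day arithmetic under AT censoring** (90 days after stop or switch, 5.1.6; 180-day latency from index, 5.1.3).
- Switcher: 0 to 90 days of empagliflozin before censoring. At 10 mg/day that is at most 10 × 90 = 900 mg (0.9 g); at 25 mg/day, 25 × 90 = 2,250 mg (2.25 g).
- Empagliflozin initiator: at risk after day 180 only if stop date + 90 > 180, that is, stop date after day 90. Duration at entry is therefore more than 90 and up to 180 days.
- So for cumulative duration, person-time below about 90 days comes essentially only from switchers, in the lowest category. Cumulative dose counts from the start of follow-up. If that means after the lag, initiators also begin near zero, so switcher time lies in the low range but does not have it to itself. For daily dose a switcher goes to 10 mg or 25 mg, whichever is recorded.

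**3. Illustrative size for duration, with censoring.** From the protocol abstract and 8.5: 16,887, 32,334 and 18,269 initiators (total 67,490); ratios 1:3, 1:1, 1:2; mean follow-up 2.4, 2.2 and 2.4 years, taken as 2.3. Assumed, because the documents give neither: switch rate r of 2%, 5% or 10% per year, and first quartile of duration Q1 of 0.8-1.2 years.
- Comparators: 16,887 × 3 + 32,334 + 18,269 × 2 = 119,533.
- Switchers: 119,533 × (1 − exp(−2.3r)) = 5,374, 12,985 or 24,560.
- Switcher person-years (PY) at 0.25 year each: 1,343, 3,246 or 6,140.
- Initiator PY below Q1, approximated as 67,490 × (Q1 − 0.5): 20,247 at Q1 = 0.8; 47,243 at Q1 = 1.2.
- Share from switchers: lowest 1,343 / (1,343 + 47,243) = 2.8%; highest 6,140 / (6,140 + 20,247) = 23.3%.

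Giving every switcher the full 0.25 year overstates the share. Treating every initiator as on treatment up to Q1 overstates initiator time and so understates it.

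**4. Events.** Planned comparator PY: 50,661 × 2.4 + 32,334 × 2.2 + 36,538 × 2.4 = 280,412. Weighting the urinary tract cancer rates (111.5, 164.5, 161.5 per 100,000 PY) by these PY gives about 141 per 100,000. Switcher time then carries about 1,343 × 0.00141 = 1.9, 3,246 × 0.00141 = 4.6 or 6,140 × 0.00141 = 8.7 cancers over three countries, and fewer for bladder or renal cancer alone. If the rate in that time were doubled, the lowest category's rate would be multiplied by 1 + share, that is 1.03 to 1.23.

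**5. Without censoring** the 90-day cap goes, and initiators who stop early also stay at risk, so the denominator changes too. I put no share on that case.

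**The case against.** The best defence is that the SAP describes only two follow-up regimes, AT and ITT. On that view the restriction in Table 4 merely separates AT from ITT, the opening of 5.1.3 supplies the general rule, and the missing daily-dose category shows that open-ended follow-up was never meant. This is probably the intention. It does not remove the conflict, because 5.1.7 ties AT to the primary definition and Table 16 puts the secondary analyses under other names.

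On switchers, the Table 6 footnote can be read as freezing the last value. Section 5.1.6 includes switching in discontinuation, so a DPP-4 initiator's last value, 'Never', would be held for the 90 days. That reading is possible. It is the less natural one, since the footnote speaks of the end of treatment and not of a first empagliflozin prescription, but the SAP should say which applies.

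Three further points stand. The reference is 'Never', so hazard ratios for higher categories are largely unaffected if AT censoring applies. Switchers have already passed 180 days from index without cancer. The documents justify the lag by induction and promotion and treat diagnostic bias separately, so a reader should not infer that the lag is stated to remove detection-driven cancers.

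SAP text between 6.7.3.2 and 6.10 is not visible and may contain a rule. The point therefore rests on the conflict between visible texts, and an unseen rule applying this censoring would still have to be reconciled with Table 4.

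**Conclusion.** The inconsistency on censoring stands. The switcher problem stands on the natural reading of Table 6, not as something that the SAP states outright. It concerns the secondary hazard ratio models and the cumulative-dose incidence rates.

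With AT censoring, switchers supply about 3-23% of person-time in the lowest duration quartile, under assumed switch rates of 2-10% per year and an assumed Q1 of 0.8-1.2 years. No such share was computed for cumulative dose or daily dose. Distortion of the low-exposure hazard ratio is plausible; its direction and size are not established.

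A reader might infer that a true gradient would be hidden or reversed. The material does not show this: it gives person-time shares built on assumed rates, about 2 to 9 expected cancers, and a factor of at most 1.23 even if the rate in switcher time doubled. The change is worth making before analysis because it fixes the risk set and the classification for all three secondary exposures at little cost.

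**What to change.** - **Table 4:** state that censoring at stop or switch plus 90 days applies to the AT analyses and to the three secondary exposure analyses.
- **Table 6:** state that patients whose index drug is a DPP-4 inhibitor stay in 'Never' until censored, including the 90 days after a first empagliflozin prescription, as in the primary analysis.

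This takes two sentences and no new data. The downside is that up to 90 days of real empagliflozin use per switcher is counted as 'Never'. On the assumptions above that is 1,343 to 6,140 PY against about 280,412 planned comparator PY, or 0.5% to 2.2% of the reference time.

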5.1.4. Days' supply and duration of exposure

The estimated days' supply of each prescription/dispensing will be used to determine exposure episodes. Continuous exposure periods will then consist of consecutive exposure episodes separated by a gap of at most 30 days (Section 5.1.6).

The construction of exposure episodes is based on the assumptions that the total prescribed/dispensed dose is consumed as 1 unit per day, 1 defined daily dosage (DDD) per day, or 1 prescribed daily dose (PDD) per day. The construction of exposure episodes using PDD exhibited better performance and led to fewer outcome misclassifications, compared to the alternative approaches [4]. In this study, the length of each exposure episode (days' supply) will be calculated at the prescription level as the total prescribed/dispensed doses divided by the daily dose.

The total doses will be calculated as the total number of product units per prescription, using corresponding variables including the package size, unit strength and prescribed number of packages. The daily dose in product units will be determined based on the PDD (or recommended daily dose) and the unit strength in the prescribed packages. For study drugs, the daily doses will be ascertained from recommended dosages and pill strength. In case of missing information, the days' supply will be estimated as the median days' supply of the same drug prescription. The available variables will be extracted from the relevant databases, as described below.

Proprietary confidential information © 2024 Boehringer Ingelheim International GmbH or one or more of its affiliated companies

UK CPRD-GOLD and Aurum

The total doses will be estimated as the total number of prescribed units using the follow variables provided by CPRD:

- Number of individual product packs prescribed
- Pack size
- Unit strength of the product

For study drugs and metformin, daily dose and days' supply will be derived from pill strength and dosage recommendations. For other drugs, the daily dose will be ascertained based on the prescribed daily dose (if available) or defined daily dose and the unit strength of the dispensed packages.

Sweden

The total doses will be calculated as the total number of dispensed units using the follow variables:

- Size of dispensed package
- Number of dispensed packages
- Drug strength

For study drugs and metformin, daily dose and days' supply will be derived from pill strength and dosage recommendations as described in Annex IV. For other drugs, the daily dose will be ascertained based on the defined daily dose and the unit strength of the dispensed packages.

Finland

The prescription information are available as purchase records, including

- ATC codes
- Number of packages prescribed
- Nordic Article Number (VNR).

VNRs will be mapped to retrieve information on the package size and unit strength of the products, using the publically available database from Finnish Medicines Agency (FIMEA). For study drugs and metformin, daily dose and days' supply will be derived from pill strength and dosage recommendations as described in Annex IV. For other drugs, the daily dose will be ascertained based on the defined daily dose and the unit strength of the dispensed packages.

